5.7.c. Describe the pathway of how the PHI will be accessed or obtained, starting with the source/location and then describing the system/path/mechanism by which it will be identified, accessed, and copied for the research. *Be specific. For example: directly view records; search through a department's clinical database; submit a request to Leaf.*

Research staff will review the patient's medical records via Epic to ensure the individual has a definitive MS diagnosis before initiating the screening process.

5.7.d. For which PHI will subjects provide HIPAA authorization before the PHI is accessed, obtained and/or used?

N/A

Confirm by checking the box that UW Medicine [HIPAA Authorization](#) form maintained on the HSD website will be used to access obtain, use, or disclose any UW Medicine PHI.

Confirmed

5.7.e. Will you obtain any HIPAA authorizations electronically (i.e., e-signature)?

No
 Yes → Confirm by checking the box that you have read and understand the *Electronic Documentation of Consent* section of the [WORKSHEET Consent Requirements and Waivers](#) the [GUIDANCE Consent Documentation of Consent](#) for information regarding the use of electronic signatures and HIPAA authorizations.

Confirmed

5.7.f. For which PHI will HIPAA authorization NOT be obtained from the subjects?

Provide the following assurances by checking the boxes.

The minimum necessary amount of PHI to accomplish the purposes described in this application will be accessed, obtained and/or used.

- The PHI will not be reused or disclosed to any other person or entity, except as required by law, for authorized oversight of the research study, or for other research for which the use or disclosure of PHI would be permitted.
- The HIPAA “accounting for disclosures” requirement will be fulfilled, if applicable. See [UW Medicine Compliance Policy #104](#).
- There will be reasonable safeguards to protect against identifying, directly or indirectly, any patient in any report of the research.

5.8. [DETERMINATION] Genomic data sharing. Will the research obtain or generate genomic data?

No

Yes → Answer the question below.

5.8.a. Will genomic data from this research be sent to a national database (for example, NIH’s dbGaP database)?

No

Yes → Complete the [SUPPLEMENT Genomic Data Sharing](#) and upload it to [Zipline](#).

5.9. Whole genome sequencing. For research involving biospecimens: Will the research include whole genome sequencing?

Whole genome sequencing is sequencing of a human germline or somatic specimen with the intent to generate the genome or exome sequence of that specimen.

No

Yes

5.10. [DETERMINATION] Cannabis (marijuana), hemp, and related compounds. These questions are about: cannabis (any part of the plant in any form), hemp, cannabidiol (CBD), delta-8-THC, any product derived from cannabis or hemp, and related synthesized compounds. All UW research must comply with federal laws about cannabis because of conditions associated with the federal money that UW receives. Answer the questions below so that HSD can determine whether the federal laws apply to your specific situation. See the [UW Guidance on Research Involving Marijuana](#) for additional information.

5.10.a. Does your research involve any of the following? Check all that apply.

- Study staff will obtain or handle any of the above items
- Study will provide money to the participants to obtain any of the above items
- Study participants will use or consume any of the above items on campus or in any UW-owned or leased facility
- None of the above

5.10.b. If you checked any box except “None of the above”, provide the following information about each cannabis and related item your research will involve: Name of the item, how you will obtain it, the source, and whether it contains $\geq 0.3\%$ THC (tetrahydrocannabinol).

Click or tap here to enter text.

5.11. Possible secondary use or sharing of information, specimens, or subject contact information. Please consider the broadest possible future plans and whether consent will be obtained now from the subjects for future sharing or research uses (which it may not be possible to describe in detail at this time).

Many federal grants and contracts now require data or specimen sharing as a condition of funding, and many journals require data sharing as a condition of publication. "Sharing" may include (for example): informal arrangements to share banked data/specimens with other investigators; establishing a repository that will formally share with other researchers through written agreements; or sending data/specimens to a third-party repository/archive/entity such as the Social Science Open Access Repository (SSOAR), or the UCLA Ethnomusicology Archive.

Answer all of the questions below. Write **NA** in response to questions **5.11.b** through **5.11.g** if sharing is unlikely or if the only sharing will be through the NIH Genomic Data Sharing described in [question 5.8](#).

5.11.a Is this research funded by an NIH funding application submitted on or after January 25, 2023.

No

Yes → [NIH Data Management and Sharing Policy](#) applies to this research. Complete the rest of this section. If the policy applies and data will not be shared, provide the justification in response to **5.11.e** and write **NA** in response to the other questions.

5.11.b. Describe what will be stored for future use, including whether any direct or indirect (e.g., subject codes) identifiers will be stored.

All study data will be stored in de-identified form indefinitely following the closure of the IRB application. Study researchers may conduct secondary analyses of the study data in de-identified form following closure related to examining various aspects of the behavioral interventions, quality of life issues regarding individuals with MS, etc. Study data may be shared in de-identified form with outside researchers and collaborators as requested and deemed acceptable by study investigators.

5.11.c. Describe what will be shared with other researchers or with a repository/database/registry, including whether direct identifiers will be shared and (for specimens) what data will be released with the specimens. If shared through a repository, specify if it is unrestricted access (i.e., publicly accessible).

Study data may be shared in de-identified form with outside researchers and collaborators as requested and deemed acceptable by study investigators.

5.11.d. Who will oversee and/or manage the sharing?

[name], UW PI

5.11.e. Describe the possible future uses, and any limitations or restrictions on future uses or users.

Examples of limitations:

- Consent prohibits or limits the scope of sharing and use (e.g., consent states that data will be used only for cardiovascular research)
- Privacy or safety or research participants would be compromised (e.g., there is risk of reidentification and/or harm)
- Explicit federal, state, or local, or Tribal law, regulation, or policy prohibits disclosure

Document Date & Version	APPLICATION IRB Protocol	Researcher Date & Version
01.26.2023 Version 4.3		05/02/2024 Version 1.5 Page 29 of 61

- *Restrictions imposed by existing or anticipated agreements (e.g., with third party funders, partners, with repositories, medical centers providing health information under a data use agreement)*

As mentioned above, study data may be analyzed to answer both a priori and post hoc hypotheses related to various aspects of the study behavioral interventions and quality of life issues regarding individuals with MS within the context of rehabilitation medicine.

5.11.f. Consent. Will consent be obtained now from subjects for the secondary use, banking, and/or future sharing?

No

Yes → Be sure to include the information about this consent process in the consent form (if there is one) and in the answers to the consent question in Section 8.

5.11.g. Withdrawal. Will subjects be able to withdraw their data/specimens from secondary use, banking or sharing?

No

Yes → Describe how, and whether there are any limitations on withdrawal.

Example: data can be withdrawn from the repository but cannot be retrieved after they are released.

Study data cannot be withdrawn following data collection or retrieved after they are released.

5.11.h. Agreements for sharing or release. Confirm by checking the box that the sharing or release will comply with UW (and, if applicable, UW Medicine) policies that require a formal agreement with the recipient for release of data or specimens to individuals or entities other than federal databases.

Data Use Agreements or Gatekeeping forms are used for data; Material Transfer Agreements are used for specimens (or specimens plus data). Do not attach any template agreement forms; the IRB neither reviews nor approves them.

Confirmed

5.12. Communication with subjects during the study. Describe the types of communication (if any) the research team will have with already-enrolled subjects during the study. Provide a description instead of the actual materials themselves.

Examples: email, texts, phone, or letter reminders about appointments or about returning study materials such as a questionnaire; requests to confirm contact information.

Staff will email participants notifications to complete online assessments at designated times, call to administer assessments as needed and based on participant preference, check on study progress, and, if the participant is unresponsive to email, call or send text messages.

5.13. Future contact with subjects. Is there a plan to retain any contact information for subjects so that they can be contacted in the future?

No

Yes → Describe the purpose of the future contact, and whether use of the contact information will be limited to the study team; if not, describe who else could be provided with the contact information. Describe the criteria for approving requests for information.

Examples: inform subjects about other studies; ask subjects for additional information or medical record access that is not currently part of the study proposed in this application; obtain another sample.

We would like to retain contact information so if a participant is interested in published results, we may notify them or send them information about the results.

In addition, study staff may share direct identifiers with other UW Department of Rehabilitation Medicine researchers if a participant indicates they would like to be enrolled in the department subject pool and contacted regarding future opportunities to participate in research.

5.14. Alternatives to participation. Are there any alternative procedures or treatments that might be advantageous to the subjects?

If there are no alternative procedures or treatments, select "No". Examples of advantageous alternatives: earning extra class credit in some time-equivalent way other than research participation; obtaining supportive care or a standard clinical treatment from a health care provider instead of participating in research with an experimental drug.

No

Yes → Describe the alternatives.

Click or tap here to enter text.

5.15. Upload to Zipline all data collection forms (if any) that will be directly used by or with the subjects, and any scripts/talking points that will be used to collect the data. Do not include data collection forms that will be used to abstract data from other sources (such as medical or academic records), or video recordings.

- *Examples: survey, questionnaires, subject logs or diaries, focus group questions.*
- *NOTE: Sometimes the IRB can approve the general content of surveys and other data collection instruments rather than the specific form itself. This prevents the need to submit a modification request for future minor changes that do not add new topics or increase the sensitivity of the questions. To request this general approval, use the text box below to identify the questionnaires/surveys/ etc. for which you are seeking this more general approval. Then briefly describe the scope of the topics that will be covered and the most personal and sensitive questions. The HSD staff person who screens this application will let you know whether this is sufficient or whether you will need to provide more information.*
- *For materials that cannot be uploaded: upload screenshots or written descriptions that are sufficient to enable the IRB to understand the types of data that will be collected and the nature of the experience for the participant. You may also provide URLs (website addresses) or written descriptions below. Examples of materials that usually cannot be uploaded: mobile apps; computer-administered test; licensed and restricted standardized tests.*
- *For data that will be gathered in an evolving way: This refers to data collection/questions that are not pre-determined but rather are shaped during interactions with participants in response to observations and responses made during those interactions. If this applies to the proposed research, provide a description of the process by which the data collection/questions will be established during the interactions with subjects, how the data collection/questions will be documented, the topics likely to be addressed, the most sensitive type of information likely to be gathered, and the limitations (if any) on topics that will be raised or pursued.*

Use this text box (if desired) to provide:

- Short written descriptions of materials that cannot be uploaded, such as URLs
- A description of the process that will be used for data that will be gathered in an evolving way.
- The general content of questionnaires, surveys and similar instruments for which general approval is being sought. (See the **NOTE** bullet point in the instructions above.)

See uploaded documents.

5.16. [DETERMINATION] SARS-CoV-2 testing. Will the subjects be tested for the SARS-CoV-2 coronavirus?

No

Yes → If yes:

- Name the testing lab
- Confirm that the lab and its use of this test is CLIA certified or certified by the Washington State Department of Health
- Describe whether you will return the results to the participants and, if yes, who will do it and how (including any information you would provide to subjects with positive test results).

Click or tap here to enter text.

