First, we will develop and pilot test three telehealth cognitive behavioral therapy (CBT) components for fatigue in PwMS to maximize feasibility and acceptability. We will create treatment manuals and participant materials for the following three CBT components for PwMS and fatigue:

1. *Relaxation training* (n=7): Didactic and experiential training in one or more relaxation techniques such as diaphragmatic breathing, progressive muscle relaxation, autogenic relaxation, and guided imagery
2. *Behavioral activation* (n=7): Didactic material and practice focused on identification and reduction of avoidance behaviors (e.g., excessive rest) and increased engagement in valued and reinforcing activities (e.g., physical activity, social engagement)
3. *Cognitive therapy* (n=7): Didactic material and practice focused on identifying, challenging, and modifying inaccurate and/or unhelpful patterns of thought about the self and the world (e.g., catastrophizing the meaning and consequences of fatigue) to change unwanted behavioral patterns (e.g., excessive rest)

Next, we will recruit, enroll, and randomize 21 participants. Participants will complete the baseline self-report assessment via REDCap (or by telephone, if preferred). Study staff will randomly assign them to one of three CBT intervention components noted above.

We will test each of the three components with seven fatigued PwMS (N=21) and evaluate the feasibility, acceptability, and preliminary efficacy of each component. Participants will complete the 4-session telehealth treatments by telephone or UW Zoom [Health Insurance Portability and Accountability Act (HIPAA)-compliant].

Participants will complete patient-reported outcome measures (PROMs) for pre- and post-intervention assessments via REDCap (or by telephone, if preferred). During the pre- and post-intervention assessments time periods, participants will also complete a survey consisting of four to eight questions

about their fatigue twice per day (morning and evening) for seven days via REDCap (or by telephone, if preferred). They will also complete a treatment expectancy measure after the first session via REDCap (or by telephone, if preferred). They will complete qualitative semi-structured interviews at post-intervention to contextualize quantitative data and refine the components. They will also complete a medication form by phone at the pre-treatment and post-treatment timepoints.

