All study activities will be completed remotely via Zoom or over the phone over the approximately 2 months. Participants will complete a baseline self-report assessment via REDCap (or by telephone, if preferred) that will take approximately 30-45 minutes to complete. At this time, they will also complete a medication collection form with research staff by phone and will be randomly assigned to one of three 4-session telehealth CBT intervention components: (1) relaxation training, (2) behavioral activation, or (3) cognitive therapy. Prior to starting their assigned intervention component, participants will complete a survey consisting of four to eight questions about their fatigue twice per day (morning and evening) for seven days via REDCap (or by telephone, if preferred). They will then complete the 4-session intervention to which they are randomly assigned in approximately 4 weeks. After completing the first intervention session, participants will complete a treatment expectancy measure via REDCap (or by telephone, if preferred). After completing the intervention, participants will complete the post-intervention self-report assessment via REDCap (or by telephone, if preferred) within one month of the last intervention session. During this time, they will also complete a medication collection form with research staff by phone and a survey consisting of four to eight questions about their fatigue twice per day (morning and evening) for seven days via REDCap (or by telephone, if preferred). Qualitative interview data will supplement the quantitative data collected in the post-intervention assessment. Study staff will conduct and audio record semi-structured interviews within one month of completing the last intervention session to query participants about feasibility, acceptability, appropriateness, and perceived efficacy of the intervention component they completed to inform potential component refinement.

5.2. **[DETERMINATION] Recordings.** Does the research involve creating audio or video recordings?

No → Go to [question 5.3](#).

Document Date & Version	APPLICATION IRB Protocol	Researcher Date & Version
01.26.2023 Version 4.3		05/02/2024 Version 1.5 Page 21 of 61

Yes → Verify that you have described what will be recorded in the answer to [question 5.1.](#), and answer question the question below.

5.2.a. Before recording, will consent for being recorded be obtained from subjects and any other individuals who may be recorded?

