After providing informed consent, research staff will ask the participant to provide demographic data (e.g., age, sex, gender orientation, ethnicity/race, marital status, education level, income, household size, disability compensation status, lawsuit status, employment status) for descriptive purposes. We will also ask participants to complete validated self-report questionnaires (demographics, MS disease-related variables, quality of life, and biopsychosocial symptom variables [e.g., fatigue]). We will also ask participants to complete a survey consisting of four-eight questions about their fatigue twice per day (morning and evening) for seven days (each survey should take less than 5 minutes).

Personal Contact Information

Research staff will collect the following information from participants: (1) contact information; (2) preferred telephone number to reach an individual if they have more than one line; (3) permission to leave message on mobile/landline phones; (4) permission to send a text message and, if yes, cell phone carrier; (5) best times/days to reach participant; (6) email address; (7) preferred communication method; and (8) names and contact information of people staff are allowed to contact if participant is lost to follow-up or otherwise cannot be contacted (i.e., collateral contacts).

We will gather data either from the participant directly or in the form of online self-report assessments via a password-protected database on the department's secure server.

Treatment Expectancy Assessment

Participants will complete the Credibility/Expectancy Scale after the first intervention session.

Medication collection form (pre- and post-treatment)

Participants will be asked questions about the medications they are taking (e.g., name, indication, dosage, dose units)

Post-Intervention Assessment

Participants will be asked questions about quality of life and biopsychosocial symptom variables (e.g., fatigue). We will also ask participants to complete a survey consisting of four-eight questions about their fatigue twice per day (morning and evening) for seven days (each survey should take less than 5 minutes).

Post-Intervention Qualitative Interview

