10. RISK / BENEFIT ASSESSMENT

10.1. [DETERMINATION] Anticipated risks. Describe the anticipated risks of harm, discomforts, and hazards to the subjects and others of the research procedures.

For each harm, discomfort, or hazard:

- Describe the magnitude, probability, duration, and/or reversibility of the harm, discomfort, or hazard, AND
- Describe how the risks will be reduced or managed. Do not describe data security protections here, these are already described in [question 9.6.](#)
- Consider possible physical, psychological, social, legal, and economic harms, including possible negative effects on financial standing, employability, insurability, educational advancement, or reputation. For example, a breach of confidentiality might have these effects.
- Examples of "others": embryo, fetus, or nursing child; family members; a specific group.
- Ensure applicable risk information from any Investigator Brochures, Drug Package Inserts, and/or Device Manuals is included in your description.
- Do not include the risks of non-research procedures that are already being performed.
- If the study design specifies that subjects will be assigned to a specific condition or intervention, then the condition or intervention is a research procedure - even if it is a standard of care.
- Examples of mitigation strategies: inclusion/exclusion criteria; taking blood samples to monitor something that indicates drug toxicity.
- Review [GUIDANCE Consent Identifying and Describing Reasonably Foreseeable Risks in Research](#) for information about which risks should be described in the consent process/form.
- As with all questions on this application, you may refer to uploaded documents.

General/Reaction to Assessments

Participants may experience fatigue and/or boredom while completing the assessments, qualitative interview and/or the treatment sessions.

Some participants may also experience mild anxiety, frustration, and/or stress while answering sensitive questions about fatigue and mood. As a result of answering questions about fatigue, some

Document Date & Version	APPLICATION IRB Protocol	Researcher Date & Version
01.26.2023 Version 4.3		05/02/2024 Version 1.5 Page 51 of 61

participants may focus more on their fatigue, which may lead to a temporary increase in fatigue intensity.

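### Section 5.1 randomises participants before the seven-day baseline fatigue diary and does not keep the component undisclosed until the diary ends

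*Protocol*

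**What the plan says.** Protocol section 5.1 sets out the sequence for each participant. The baseline questionnaire comes first. At the same stage a medication form is completed by phone and participants "will be randomly assigned to one of three 4-session telehealth CBT intervention components". The daily diary follows: "Prior to starting their assigned intervention component, participants will complete a survey consisting of four to eight questions about their fatigue twice per day", for seven days. The sessions come last: "They will then complete the 4-session intervention to which they are randomly assigned in approximately 4 weeks".

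Section 1.5 also places assignment directly after the baseline self-report assessment: "Study staff will randomly assign them to one of three CBT intervention components noted above". It gives the diary the role of a before-and-after measure: "During the pre- and post-intervention assessments time periods, participants will also complete a survey consisting of four to eight questions". Section 5.4 lists the diary under the baseline assessment but gives no order relative to assignment, so it does not conflict with 5.1.

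The stated purpose in 1.5 is to "test each of the three components with seven fatigued PwMS (N=21) and evaluate the feasibility, acceptability, and preliminary efficacy of each component".

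No section says that the participant is kept unaware of the component until the diary is finished. The un-blinding question in 10.7 is answered N/A.

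**The concern.** A baseline is best completed before assignment, so that no part of it can depend on what was assigned. Here the baseline is split. The questionnaire is collected at or before assignment, and the daily diary after it. Two things follow.

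- **Ratings.** The diary consists of self-reported fatigue. A participant who has been told which component is coming may rate differently during that week, which would move the starting point of the before-and-after change for that component.
- **Places.** A person who stops during the diary week has been randomised to a component and has received none of it. With seven people per component, that loss is counted against the component although no session has taken place.

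Section 10.1 accepts that, when asked about fatigue, "participants may focus more on their fatigue, which may lead to a temporary increase in fatigue intensity". That sentence concerns the effect of being asked, not of knowing the component. It supports only the limited statement that these ratings are reactive.

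**Working it through.** **Sequence.** The steps as 5.1 orders them:

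| Step | Relative to assignment |
|---|---|
| Baseline questionnaire | at or before |
| Medication form by phone, random assignment | same contact stage |
| Seven-day diary, morning and evening | after |
| Four sessions over about four weeks | after the diary |

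The diary sentence already speaks of an assigned component, so the order does not depend on one ambiguous word. Section 1.5 agrees, and no section gives the reverse order. Delivery of the component does wait for the diary. What is missing is any statement that disclosure waits too.

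**Plan's own figure.** Three components × 7 = 21, as stated in 1.5.

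**Baseline entries collected after assignment.** 7 days × 2 per day = 14, which is all of the pre-intervention diary.

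**One diary-week leaver.** 1/7 = 14.3% of a component's randomised group, and 1/21 = 4.8% of the total.

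**How often this might happen.** The protocol gives no diary-week loss. Its only related figure is retention above 90% in past studies (section 4.1). Let d be the assumed chance that a randomised participant leaves in the diary week, with leavers independent. Then:

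- expected leavers = 21 × d
- chance of at least one in a given component = 1 − (1 − d)^7
- chance of at least one overall = 1 − (1 − d)^21

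The lowest row spreads a 10% loss evenly over about two months of participation: two months ≈ 8.7 weeks, so d = 10%/8.7 ≈ 1.15% per week.

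| Assumed d | Expected leavers of 21 | At least one in a given component of 7 | At least one of 21 |
|---|---|---|---|
| 1.15% | 0.24 | 8% | 22% |
| 2% | 0.42 | 13% | 35% |
| 5% | 1.05 | 30% | 66% |
| 10% | 2.10 | 52% | 89% |

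The 10% row needs all of the past loss to have fallen in this single week, so it is an extreme case.

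**With assignment after the diary.** All 14 entries precede any knowledge of the component, diary-week leavers are not randomised, and all 21 randomised people are at the point of starting a component.

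**Rating shift.** No calculation is possible; the protocol contains nothing from which a size could be derived.

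**The case against.** The case for leaving the text alone is reasonable. The protocol calls the diary a pre-intervention measure, and that is what it is; nowhere does it promise a pre-randomisation diary, so nothing is contradicted. It does not say that participants are told their component at assignment. Staff are trained on a manual of procedures (section 12.4), not shown here, which may settle the timing. Section 1.6 describes a prospective case series, and 1.8.a gives feasibility and acceptability as its focus. All three groups receive an active component, so there is no control group to disappoint. A gap between assignment and first treatment is common, and reordering would not prevent anyone from leaving. If participants did know their component, leaving before session 1 could itself say something about acceptability.

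Most of this stands, and it limits the size of the point. It does not make the present order as good as the alternative. Section 5.1 fixes the order, so this is not just a detail left for another document. The expectancy measure comes after session 1 and so cannot show what participants expected during the diary week.

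A reader might go further and infer that the diary baseline is biased. The document does not support that: immediate disclosure is not stated, and the N/A in 10.7 shows only that no blinding procedure is described. A reader might also compare the time spent on the diary, where 5.4 says "for seven days (each survey should take less than 5 minutes", with the time spent on the questionnaire, as a gauge of the damage. Minutes of form-filling do not measure bias, and no such share is used here. Nor is the 14 points per leaver an effect of the ordering. It reflects the arm size; the order decides only whether that person is counted in an arm.

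**Conclusion.** The point holds as a low-cost improvement and not as a demonstrated flaw. Assignment precedes the baseline diary by explicit text, and no safeguard on disclosure is stated. Influence on the ratings is possible, not shown, and cannot be quantified. The loss of places is real in kind and probably small in number: about a quarter of a person expected if past loss was near 10% and spread evenly, and about two people only in the extreme case.

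This rests on two assumptions. The diary-week loss rates are assumed. A leaver is also taken not to be replaced: 1.5 randomises 21, and no section provides for replacement. Section 2.9 does give 21 in answer to a question about people who will complete the research; if replacement was intended, the lost-place limb weakens and the disclosure limb remains.

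The consequence stays modest because the diary is wholly pre-treatment, a questionnaire fatigue baseline exists at or before assignment, and no between-component test is stated.

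**What to change.** In 5.1, move the assignment step to after the diary. For example: after the seven-day baseline diary is complete and before session 1, study staff randomly assign the participant and tell them their component. Make the order in 1.5 match.

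If early assignment is needed to book sessions, keep it and add one sentence saying that the component is not disclosed to the participant until the diary is finished. This protects the ratings but not the places, since a diary-week leaver would still be randomised.

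The cost is a reordered step in two sections. Session scheduling waits for the diary, or one short extra contact is needed, which can be combined with booking session 1. The change does not reduce the number of people who leave in the diary week.
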